## Keratoconus and IOP Elevation Study

As part of the routine examination, pupils will be dilated using dilating drops (tropicamide and/or phenylephrine hydrochloride). As part of routine clinical IOP measurement, numbing drops (proparacaine) will be used. In cases where the clinical evaluation did not include pupil dilation and pupil size prevents ocular imaging, dilating drops might be used for the purpose of imaging in the study.

All procedures will be performed by clinical or research staff.

**Experimental procedure:** The IOP will be measured with the Goldman applanation tonometer, and then the IOP will be increased using an ODM. Proparacaine drops, which are widely used during routine eye examinations, will be used during this procedure to numb the eye while the IOP is measured. ODM is an FDA approved device that allows an increase of force on the eye in a controlled fashion and is routinely used as part of neurophthalmic evaluation. Forces will be imposed on the eye while Goldman tonometry is used to measure the IOP to reach the target IOP between 20-35 mmHg. The procedure will take five minutes.

OCT scanning will be obtained at baseline and with increased IOP. The IOP elevation will last no longer than two minutes, during which scans will be acquired by the imaging device. This stage will take 10 minutes.

The subject will be tested by clinical or research staff under the direct supervision and direction of the principal investigator or co-investigators. All devices in this study are FDA-approved with the exception of the investigational OCT devices and multi-modal adaptive optics system; see Appendix). None of the systems in this study are considered investigational, nor do any of the devices produce harmful radiation.

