## Keratoconus and IOP Elevation Study

### Study Summary

Title	Optic Nerve Head Structural Response to IOP Elevation in Patients with Keratoconus
Short Title	Keratoconus and IOP elevation Study
IRB Number	17-01360
Study Type	Human study
Study Design	Prospective experimental study
Study Intervention	In-vivo investigation of ocular structure in eyes with keratoconus under elevated intraocular pressure
Study Duration	Indefinite
Study Location(s)	NYU Department of Ophthalmology: Faculty Group Practice
Primary Objective	To examine in-vivo how lamina cribrosa in subjects with keratoconus respond to increasing intraocular pressure
Sample Size	230 subjects
Diagnosis and Main Inclusion Criteria	Subjects diagnosed with keratoconus or glaucoma
Control / Comparison	None
Statistical Methodology	Mixed effect models for the comparison between keratoconus and glaucomatous eyes

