### **2. Study Objectives**

To study the differences in optic nerve microstructure and biomechanical features between keratoconus and glaucomatous eyes. We hypothesize that subjects with keratoconus have an abnormal biomechanical response of the lamina cribrosa in response to IOP modulation.

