### Devices

#### 1. Ophthalmodynamometer

The ODM (Baillart ophthalmodynamometer, W. Koch Optik, Zurich, Switzerland) is a disc attached to a piston that induces a controlled force on a fixed area. The device will be used to apply a pressure within the range of 20 mmHg - 35 mmHg 4 times to each eye. Each increase of pressure will last approximately 30 seconds. The device is FDA approved and will be used as routinely used in clinical practice.

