### 6. Statistical Plan

The data will be divided into two groups according to the clinical diagnosis: subjects with keratoconus and with glaucoma. Baseline ONH location and shape will be compared to IOP stressed location and shape by mixed effect models.

Based on unpublished pilot data, an increase in cup depth of approximately  $13\mu\text{m}$  in response to acute IOP elevation is anticipated. To detect a difference of  $13\mu\text{m}$  in cup depth with an experimental error of  $0.07\mu\text{m}$ , a sample of 230 subjects with keratoconus and glaucoma has a power of 80% (5% level of significance).

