### Analysis Methods

The ONH and peripapillary region scans by OCT will be evaluated for tissue deformation, decrease in the rim area, increase in cup depth and changes in the lamina cribrosa structure. . Outcome measures will evaluate the aforementioned expected deformations of the LC in microns. These micron measurements will be obtained from in vivo OCT images. Cornea will be evaluated for anterior and posterior curvatures, aberrations, pachymetry and hysteresis.

Mixed effect models will be used for longitudinal analysis accounting for the use of information from both eyes for some subjects. Custom analysis techniques will be utilized to measure differences in ocular structures, especially the LC, under different pressure conditions.

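### IOP is raised to an absolute level and the analysis names no IOP-rise term, so any cohort difference in mean rise would be mixed into the keratoconus-versus-glaucoma comparison

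*Combined protocol and SAP*

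**What the plan says.** **Stimulus.** Section 5, Experimental procedure, has IOP measured at baseline and then raised with the ophthalmodynamometer: "Forces will be imposed on the eye while Goldman tonometry is used to measure the IOP to reach the target IOP between 20-35 mmHg". Scans are taken at baseline and during elevation: "The IOP elevation will last no longer than two minutes, during which scans will be acquired by the imaging device". The device description in the same section adds: "The device will be used to apply a pressure within the range of 20 mmHg - 35 mmHg 4 times to each eye". It does not say whether the four levels are the same or stepped, or whether they are common to all eyes.

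**Cohorts.** Section 3 describes the study as non-randomised. The inclusion and exclusion criteria in Section 4 set no limit on baseline IOP and no matching on it. The planned size is 115 subjects per cohort.

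**Analysis.** Section 6 states: "Baseline ONH location and shape will be compared to IOP stressed location and shape by mixed effect models". Under Analysis Methods it adds: "Mixed effect models will be used for longitudinal analysis accounting for the use of information from both eyes for some subjects", and "Custom analysis techniques will be utilized to measure differences in ocular structures, especially the LC, under different pressure conditions". Baseline IOP, achieved IOP and IOP rise are not named as model terms, and no per-mmHg outcome is defined.

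**Contrast.** The Study Summary gives the methodology as "Mixed effect models for the comparison between keratoconus and glaucomatous eyes", and the objective in Section 2 is "To study the differences in optic nerve microstructure and biomechanical features between keratoconus and glaucomatous eyes".

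**The concern.** A biomechanical response is deformation relative to load. Here the load is the IOP rise, which equals the level reached minus that eye's baseline. Nothing in the design makes the mean rise equal in the two cohorts, and nothing written in the analysis adjusts for it.

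The hypothesis is an abnormal lamina response in keratoconus. If one cohort receives the larger rise, equally compliant tissue could be reported as responding abnormally. If the imbalance runs the other way, a real difference could be hidden. This is bias, so a larger sample does not remove it.

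**Working it through.** **1. Rise available to an eye (baselines assumed).** Rise = level reached − baseline.
- Baseline 10 mmHg: 20 − 10 = 10 to 35 − 10 = 25 mmHg.
- Baseline 15 mmHg: 5 to 20 mmHg.
- Baseline 19 mmHg: 1 to 16 mmHg.

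**2. An SD for the illustration.** Section 6 gives 13 µm, an experimental error of 0.07 µm, 230 subjects, 80% power and 5% significance. These figures do not reproduce 230: with an SD of 0.07 µm the formula asks for 1 subject per cohort. That is a separate matter, but it means the SD has to be back-solved (two-sided, 1.960 + 0.842 = 2.802):
- 230 as one pooled within-eye comparison: SD = 13 × √230 / 2.802 = 70.4 µm. This is close to reading 0.07 as millimetres: (2.802 × 70/13)² gives 228 subjects.
- 230 as 115 versus 115: SD = 13 / (2.802 × √(2/115)) = 35.2 µm. This matches no printed figure.

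**3. Bias if pressure is coded only as baseline or stressed.** Assumed: response of 1 µm per mmHg in both cohorts (no true difference), levels uniform on 20–35 mmHg, baseline SD 3 mmHg, one value per subject.
- Bias ≈ slope × gap in mean rise. A 4 mmHg baseline gap gives 1 × 4 = 4 µm.
- Variance of the rise = 15²/12 + 3² = 27.75.
- At SD 70.4: total SD = √(70.4² + 27.75) = 70.6; SE = 70.6 × √(2/115) = 9.31; bias/SE = 4/9.31 = 0.43; rejection = P(Z > 1.53) + P(Z < −2.39) = 0.063 + 0.008 = 7.1%.
- At SD 35.2: total SD = 35.6; SE = 4.69; bias/SE = 0.85; rejection = 0.134 + 0.0025 = 13.6%.

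Simulation with 20,000 replicates, mean baseline 15 mmHg and the level forced at least 1 mmHg above baseline, gave:

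| Baseline gap (mmHg) | Bias (µm) | Two-state, SD 70.4 | Two-state, SD 35.2 |
|---|---|---|---|
| 0 | 0 | 5.0% | 5.1% |
| 2 | about 2 | 5.7% | 6.9% |
| 4 | about 4 | 7.1% | 13.1% |
| 6 | about 6 | 9.2% | 22.5% |

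A per-mmHg model gave 4.8–5.1% throughout.

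**4. Would common steps cure it?** No. If every eye were stepped through 20/25/30/35, the average level would be 27.5 mmHg for all and the baseline gap would still pass into the rise. The simulated bias was 1.9/3.7/5.4 µm for gaps of 2/4/6 mmHg.

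**5. Masking.** With true slopes of 2 and 1 µm per mmHg in keratoconus and glaucoma, and glaucoma baseline 4 mmHg lower, two-state power fell from 27% to 14% (SD 70.4) or from 75% to 43% (SD 35.2). The per-mmHg model went from 31% to 36%, or from 83% to 90%.

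**6. Checks on the remedy.** These used REML mixed models with 1,000 replicates, four loads per eye, both eyes in half the subjects and an assumed error of 10 µm.
- *Random effects.* With no true difference and slope SDs (subject/eye) of 0.5/0.25 or 1.0/0.5, random intercepts alone rejected 15.4% or 27.4%. Adding random slopes gave 5.7% or 4.0%, and 5.1% or 5.2% at a 4 mmHg gap.
- *Baseline IOP.* If the slope itself falls with baseline IOP (assumed 0.05 µm/mmHg per mmHg), a baseline main effect alone rejected 35.0% at a 4 mmHg gap. Adding baseline IOP × IOP rise gave 4.9%.

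**The case against.** **The plan is silent rather than wrong.** Section 6 gives no coding for pressure, its reference to different pressure conditions could cover a continuous term, and IOP is measured before and during elevation. This stands: a reader might infer that the plan rules out an IOP-rise term, and it does not. But the comparison it does describe is baseline against stressed, and the term on which the cohort contrast depends is left to choice after the data are seen.

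**No imbalance is shown.** This also stands. A reader might infer that the cohorts are known to differ in IOP, or that the direction can be guessed from the diagnosis. The documents give no IOP by cohort and support neither inference. The 2, 4 and 6 mmHg gaps are assumptions.

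**The larger error rates need the less supported SD.** The 13.1% and 22.5% figures, and the power drop from 75% to 43%, require 35.2 µm. At 70.4 µm the inflation is modest. They should not be read as the expected error of this trial.

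**Part of the plan is untouched.** The Study Summary's primary objective concerns how the lamina in keratoconus responds to rising IOP. A cohort imbalance does not confound that within-eye comparison, so a reading that the whole analysis is compromised goes too far.

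**Tonometry.** The rise is read by applanation on corneas selected for central thinning. A constant reading offset alters the rise delivered on the way to an absolute target, but it cancels from the measured rise, so a per-mmHg model accommodates it. A cohort-specific proportional error does not cancel. That is a limit of the remedy and not a reason to leave the rise out.

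**Conclusion.** The concern holds for the between-cohort comparison. The stimulus is an absolute level, baseline IOP is neither limited nor matched, allocation is not randomised, and no quantitative IOP-rise term is specified. The documents are sufficient to establish those four facts.

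The documents do not establish how much bias results. The illustrative 4 µm is 4/13 = 31% of the 13 µm on which the study was sized. It rests on an assumed linear 1 µm per mmHg and an assumed 4 mmHg gap, and it scales with both. This should be corrected before analysis. It is not evidence that the cohort contrast will be biased.

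**What to change.** **Section 6, Statistical Plan and Analysis Methods.** State that the between-cohort comparison uses a mixed model with group, continuous IOP rise from that eye's own baseline reading (zero at baseline), and group × IOP rise. Include random intercepts and random IOP-rise slopes by subject and by eye within subject, with a prespecified rule for simplifying the model if it does not converge. Make the group difference in deformation per mmHg the cohort contrast. Put baseline IOP and baseline IOP × IOP rise in that model, or in a prespecified main sensitivity analysis, because a baseline main effect alone does not correct the slope.

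**Data capture and reporting.** Record the Goldmann reading reached at each application, link it to its scan, and tabulate baseline IOP and IOP rise by cohort. Section 5 has IOP measured to reach the target but does not say that the reading is kept for each application.

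**Costs and limits.**
- The change needs SAP wording and a small data-capture step, which must be in place prospectively.
- It assumes approximate linearity, to be checked with a quadratic term. With an assumed saturating response and gaps of 2/4/6 mmHg, the per-mmHg model rejected 5.6/6.9/8.1% at an SD of 10 µm, and 4.8–5.4% at 35.2 or 70.4 µm.
- It relies on overlapping rises between the cohorts.
- It does not correct a cohort-specific proportional tonometer error, which should be reported as a limitation or explored in an optional sensitivity analysis.

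**Separately,** Section 5 treats 20–35 mmHg as the IOP reached under Experimental procedure and as the pressure applied under the device description. The two must be reconciled. Under neither reading is the rise fixed or modelled.

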### Devices

#### 1. Ophthalmodynamometer

The ODM (Baillart ophthalmodynamometer, W. Koch Optik, Zurich, Switzerland) is a disc attached to a piston that induces a controlled force on a fixed area. The device will be used to apply a pressure within the range of 20 mmHg - 35 mmHg 4 times to each eye. Each increase of pressure will last approximately 30 seconds. The device is FDA approved and will be used as routinely used in clinical practice.

#### 2. Goldmann Applanation Tonometer

The Goldmann applanation tonometer (Haag-Streit, Basel, Switzerland) measures the IOP after the eye is numbed with a drop of anesthetic (proparacaine), which is approved by the FDA. Proparacaine is part of routine patient care using a tonometer regardless of participation in this study. The instrument's tip lightly touches the surface of the cornea and the IOP is measured. The device is FDA approved is routinely used in clinical practice.

#### 3. Pentacam

## Keratoconus and IOP Elevation Study

This device (Pentacam HR; Oculus Optikgerate GmbH, Wetzlar, Germany) maps the cornea and provides pachymetry, topography and corneal aberration maps. The device is FDA approved and routinely used in clinical practice.

### 4. ORA

ORA (Reichert Corp, Buffalo NY) is an air puff tonometer that applies controlled force to flattens the cornea and provides the corneal hysteresis and corneal resistance factor. The device is FDA approved and routinely used in clinical practice.

### 5. Optical Coherence Tomography (OCT)

OCT is a non-contact, real-time, high resolution, and reproducible imaging modality that provides in-vivo optical cross-sectional scanning of the retina, the ONH and of the anterior segment structures including the cornea. Some are FDA approved and used for their approved indications. The other OCT systems and the multi-modal adaptive optics system used in this study have not been approved by the FDA, but are not being used in a way that would cause significant risk to subjects. Their use is for obtaining physiologic data, not for clinical investigation. Clinical staff will perform subject testing, not research coordinators. Information about these non-FDA approved OCTs and the multi-modal adaptive optics system can be found in appendices. With all devices, the participant sits in a slit lamp like frame. A low power laser light is projected toward the back of their eyes while the subject fixates on a target. None of the systems produce harmful radioactive radiation.

### 6. Statistical Plan

The data will be divided into two groups according to the clinical diagnosis: subjects with keratoconus and with glaucoma. Baseline ONH location and shape will be compared to IOP stressed location and shape by mixed effect models.

Based on unpublished pilot data, an increase in cup depth of approximately  $13\mu\text{m}$  in response to acute IOP elevation is anticipated. To detect a difference of  $13\mu\text{m}$  in cup depth with an experimental error of  $0.07\mu\text{m}$ , a sample of 230 subjects with keratoconus and glaucoma has a power of 80% (5% level of significance).

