Optical coherence tomography (OCT) enables tissue pathology to be imaged *in situ* and in real time with a resolution approaching that of conventional histopathology, but without the need for excising and processing specimens. Over the course of the years, we and other groups have demonstrated the excellent diagnostic ability of OCT, and the technology has become the cornerstone of clinical management in ophthalmology worldwide and the number of publications using this technology has soared exponentially in recent years (10, 11). OCT has been approved by the Food and Drug Administration for use in ophthalmology. The device provides accurate and reproducible measurements of tissues of interest in the eye (12). These properties enable improved diagnosis and longitudinal assessment for ocular disease such as glaucoma, age related macular degeneration (AMD), diabetic retinopathy (DR) and macular edema (13-16). Extensive studies have been performed with OCT examining both cross-sectional as well as longitudinal patient populations (17). Our group has published more than 100 peer-reviewed manuscripts focusing on the use of this technology in ocular diseases (18, 19).

Considering that the cornea and the LC are predominantly composed by collagen and elastin fibers, the defective corneal properties might also affect the LC reflected by abnormal response to biomechanical modulation. In the present project, our objective is to evaluate with OCT of the optic nerve head the response to IOP elevation in eyes with keratoconus, with glaucoma and in controls using commercial and prototype ophthalmic OCT imaging instruments in order

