### **4. Participant Selection, Enrollment, and Withdrawal**

#### **Study Population**

We aim to enroll 230 subjects including subjects diagnosed with keratoconus or glaucoma (115 in each cohort). There will be no enrollment restrictions based on gender, ethnic origin or HIV status and the study population will reflect the demographics of NYU Department of Ophthalmology.

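### Section 6 specifies only a baseline-versus-stressed comparison: the keratoconus-versus-glaucoma contrast is left unspecified, and the 80% power is not shown to cover it

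*Combined protocol and SAP*

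**What the plan says.** The combined protocol and SAP states its question in several places.

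- **Section 2, Study Objectives:** the aim is "To study the differences in optic nerve microstructure and biomechanical features between keratoconus and glaucomatous eyes". The hypothesis is that "subjects with keratoconus have an abnormal biomechanical response of the lamina cribrosa in response to IOP modulation".
- **Study Summary:** the primary objective is "To examine in-vivo how lamina cribrosa in subjects with keratoconus respond to increasing intraocular pressure", which concerns keratoconus alone. The statistical methodology line reads "Mixed effect models for the comparison between keratoconus and glaucomatous eyes".
- **Study Population:** 230 subjects, "115 in each cohort".
- **Section 6, Statistical Plan:** the data are split by diagnosis, and then "Baseline ONH location and shape will be compared to IOP stressed location and shape by mixed effect models". The sample-size text expects a cup-depth increase of about 13 µm under acute pressure elevation, from unpublished pilot data. It claims 80% power at the 5% level to detect a 13 µm difference in cup depth with 230 subjects and an experimental error of 0.07 µm. It does not say between what the difference lies.
- **Section 6, Analysis Methods:** mixed models serve longitudinal analysis and allow for two eyes in some subjects. The differences mentioned are between pressure conditions. Rim area, cup depth and lamina changes are listed, and the next sentence says the outcome measures evaluate those expected lamina deformations in microns. No measure is called primary.

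**The concern.** A baseline-versus-stressed comparison estimates how far tissue moves under pressure. If keratoconus eyes move by a and glaucomatous eyes by b, it can show that a and b (or their average) differ from zero. The Section 2 objective concerns a − b. Both changes can be clearly non-zero while a − b is nil, and one can reach significance and the other not without any evidence that they differ. The between-group objective needs a group-by-pressure term, and Section 6 does not write one.

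The power statement has the same gap. Its 13 µm is introduced as a response to pressure, and no expected difference between the groups is given. A reader cannot tell whether the 80% refers to the response, the group difference, or neither. With no contrast and no primary measure fixed, the model term and endpoint that answer Section 2 could be chosen after the data are seen.

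**Working it through.** **Inputs.** From Section 6: difference 13 µm, error 0.07 µm, N = 230, power 80%, level 5%. From Study Population: 115 per group. Assumed here: a two-sided test (the plan does not say) and one value per subject.

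**Step 1. The plan's own figure.** Read the printed error as the SD of change; 13/0.07 = 185.7 SDs.

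- Two groups: SE = 0.07 × √(2/115) = 0.0092 µm. Required n per group = 2 × (0.07 × (1.960 + 0.842)/13)² = 0.0005, so 1 per group.
- Paired, pooled: SE = 0.07/√230 = 0.0046 µm. Required n is 1.
- Power is about 100% in both cases, and a one-sided test gives the same result. Neither 80% nor 230 is reproduced for any contrast.

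**Step 2. The SD that would give 80% for 13 µm** (t-test, two-sided 5%).

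- Group difference in change, 115 vs 115: the detectable difference is 0.371 SD, so SD = 13/0.371 = 35.0 µm.
- Pooled paired change, n = 230: SD = 70.1 µm.
- Paired change within keratoconus, n = 115: SD = 49.3 µm.

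The variance of the group difference is SD² × 2/115 and that of the pooled mean change is SD²/230. The ratio is 4, so the group contrast tolerates only half the SD.

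**Step 3. Precision of the group contrast, 115 vs 115.** The SDs are assumptions; the documents give no usable value.

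| Assumed SD of change (µm) | Detectable at 80% (µm) | Power for 13 µm | Power for 6.5 µm |
|---|---|---|---|
| 20 | 7.4 | 99.8% | 69% |
| 30 | 11.1 | 91% | 37% |
| 35 | 13.0 | 80% | 29% |
| 50 | 18.5 | 50% | 17% |
| 70 | 26.0 | 29% | 11% |

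The 6.5 µm column is half the expected response and is only illustrative.

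**Step 4. If 0.07 was meant in millimetres (70 µm).** This is an assumption. A pooled paired t-test then needs n = 229.5, so 230, and has 80.1% power at 230. That matches the plan, but as a test of the response to pressure in both diagnoses together. On the same SD, the group contrast has 29% power for 13 µm and would need about 456 per group for 80%.

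**The case against.** The strongest reply is that the comparison is planned. The Study Summary names it, Section 6 opens by forming the two groups, and a mixed model with group and pressure is the natural reading of the two together. This stands in part. A reader might infer that the plan contains no between-group comparison at all, and the documents do not support that. The intent is there; the outcome, model term and effect size are not.

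A second reply is that the power range proves nothing, because the SDs are assumed. That also stands. A reader might infer from Step 4 that the group comparison is underpowered. The documents do not support this: the millimetre reading is an inference from arithmetic, and at an SD of 35 µm or less the group contrast has 80% power or more for 13 µm. In the plan's favour, a reader might average the pressure applications, made "4 times to each eye", to reach a smaller SD. The documents do not say that cup depth is measured at each application or that the four are independent, so this cannot establish the 80% either.

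A third reply is that cup depth may itself be the lamina measure, since Analysis Methods calls the listed changes lamina deformations in microns. That wording is ambiguous. It rules out saying that the power calculation uses the wrong endpoint; what remains is that no primary measure is named.

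Finally, the entry of None under Control / Comparison may only mean no healthy control arm, and the Background phrase "the response to IOP elevation in eyes with keratoconus, with glaucoma and in controls" is introductory text. The point does not rest on either.

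**Conclusion.** The point holds and should be fixed. Section 6 writes one comparison, and that comparison cannot answer the between-group objective of Section 2. It does address the keratoconus-only objective in the Study Summary, and the documents do not settle which of the two is primary. The stated 80% does not follow from its printed inputs for any contrast and is not shown to apply to the group difference.

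The size is conditional. With 115 per group, a two-sided 5% test and one value per subject, the detectable group difference at 80% power is 0.37 SD of change. Whether that is adequate depends on an SD the documents do not usably give; about 35 µm is the dividing value for a 13 µm difference. Correlation between two eyes and dropout are not included. Confidence is high on the missing specification and the failure to reproduce the 80%; no loss of power is established.

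**What to change.** 1. State whether the within-keratoconus response (Study Summary) or the group difference (Section 2) is primary, and align the two sections.
2. In Section 6, name one primary measure and say whether cup depth is meant as a lamina measure. On that measure, write two group contrasts in the mixed model already planned for both eyes. For the biomechanical part of Section 2, use the group-by-pressure contrast: keratoconus minus glaucoma difference in change, with a 95% CI. For the microstructure part, use the between-group difference at baseline. Include the achieved IOP rise as a covariate: the target is a range (20-35 mmHg), so an unequal rise could otherwise be mistaken for an unequal tissue response. Keep baseline versus stressed within keratoconus for the Study Summary objective.
3. Correct the 0.07 µm and say what it measures. State which comparison the 80% refers to, and give the power or detectable difference at 115 per group for the group contrast from the pilot SD of change.

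The cost is wording and contrasts on data already planned, with no added enrolment or procedures. The downside is that the stated precision may become less favourable: if the SD of change exceeds about 35 µm, the protocol would have to report less than 80% power for a 13 µm group difference.

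### The sample-size inputs do not give the stated 80% power: a variability of 0.07 µm against a 13 µm difference is either not the SD or is 500 to 1,000 times too small (two-sided 5% test)

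*Combined protocol and SAP*

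**What the plan says.** The sample-size paragraph in Section 6 (Statistical Plan) has four elements:

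- **Effect.** Unpublished pilot data suggest that cup depth will increase by about 13 µm, a change that "in response to acute IOP elevation is anticipated".
- **Variability.** The difference to be detected is 13 µm "in cup depth with an experimental error of" 0.07 µm. The term is not defined as an SD, a standard error or a repeatability figure.
- **Result.** With these inputs, "a sample of 230 subjects with keratoconus and glaucoma has a power of 80% (5% level of significance").
- **Left out.** No test, sidedness or formula is given.

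Section 4 (Study Population) splits the 230 into "subjects diagnosed with keratoconus or glaucoma (115 in each cohort").

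The comparison of interest is described in two ways. The Study Summary gives the methodology as "Mixed effect models for the comparison between keratoconus and glaucomatous eyes", and Section 2 (Study Objectives) sets the aim as "To study the differences in optic nerve microstructure and biomechanical features between keratoconus and glaucomatous eyes". Section 6 instead describes comparing baseline with IOP-stressed measurements, and its 13 µm belongs to that within-eye change. No other section gives an SD or another basis for 230.

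**The concern.** A variability of 0.07 µm is tiny beside a 13 µm effect. Taken at face value, it would let a handful of subjects settle the question, so it cannot be the figure that led to 230 subjects and 80% power. Either the number or its unit is wrong, or it measures something other than the SD that a power calculation needs.

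This paragraph is the only justification for enrolling 230 people in a procedure that deliberately raises IOP. Section 7 lists corneal abrasion as an infrequent risk and states that participants gain no direct benefit. If the paragraph cannot be reproduced, neither an ethics committee nor a reader can judge whether 230 is too many, too few or about right. It also leaves open which question the 80% applies to: the pressure-induced change in cup depth, or the difference between cohorts named in the Study Summary and Section 2.

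**Working it through.** **Inputs.** Difference 13 µm, variability 0.07 µm, 230 subjects, 5% level and 80% power (Section 6); 115 per cohort (Section 4). Sidedness is not stated, so two-sided is assumed and one-sided is shown as well. Each subject contributes one value, the change in cup depth. Correlation between eyes is ignored because the plan gives no value for it.

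**Step 1. Try to reproduce 80% with SD = 0.07 µm.** The standardised effect is 13/0.07 = 185.7. The ratio of the difference to its standard error is:

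- two-sample, 115 v 115: 13 / (0.07 × √(2/115)) = 1,408
- paired, n = 115: 13 / (0.07/√115) = 1,992
- paired, n = 230: 13 / (0.07/√230) = 2,816

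Power is essentially 100% in each case, one- or two-sided. A t-test with 2 subjects per group would already have about 100%. At 80% power the detectable difference would be 0.026 µm (two-sample) or 0.013 µm (paired, 230), not 13 µm.

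**Step 2. Try other meanings of 0.07.** Read as the standard error of the estimate, it still gives about 100%, since 13 µm is then 186 standard errors. Read as a standardised effect, it gives 18% (paired, 230) or 8% (115 v 115). Read as pure measurement error, no power can be computed, because the SD of the change across subjects is not given. None of these gives 80%.

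**Step 3. Solve for the SD that does give 80%.** By the normal approximation, two-sided, 1.960 + 0.842 = 2.802. Then:

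- two-sample, 115 v 115: SD = 13 / (2.802 × √(2/115)) = 35.2 µm
- paired, n: SD = 13 × √n / 2.802, which is 49.8 µm for n = 115 and 70.4 µm for n = 230

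The noncentral t distribution gives slightly smaller values, used from here on:

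| Test | SD for 80%, two-sided | Multiple of 0.07 µm | SD for 80%, one-sided |
|---|---|---|---|
| Two-sample, 115 v 115 | 35.0 µm | 500 | 39.5 µm |
| Paired, one cohort of 115 | 49.3 µm | 704 | 55.7 µm |
| Paired, all 230 | 70.1 µm | 1,001 | 79.1 µm |

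**Step 4. Do the sample sizes show which test was used?** They do not. At SD 35 µm the smallest two-sample size is 115 per group (80.1%; 79.7% at 114). At SD 70 µm the smallest paired size is 230 (80.1%; 79.9% at 229). These two matches are one identity: two halves of N with SD s have standard error s√(4/N) = 2s/√N, the same as a paired test on N with SD 2s.

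A value of 70 µm is 0.07 mm, so a unit slip in a pooled within-eye calculation is one possible explanation. That is an assumption which the documents do not state, and the match depends on rounding: 0.065 mm would need 199 subjects and 0.075 mm would need 264.

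**Step 5. What the candidate SDs imply at 115 per cohort, for a 13 µm difference, two-sided:**

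| SD of the change | Power within one cohort (paired, 115) | Power between cohorts (115 v 115) |
|---|---|---|
| 35 µm | 97.7% | 80.1% |
| 49.3 µm | 80.1% | 51.2% |
| 70 µm | 50.6% | 28.9% |

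At SD 70 µm the difference detectable with 80% power is 18.4 µm within one cohort and 26.0 µm between cohorts.

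**The case against.** Five points can be made for the plan.

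- **The unit may be a misprint or a file-conversion slip.** If the intended figure is 0.07 mm, a pooled paired test on 230 does give 80%. This is possible but unproven. Even if it is so, the text still needs correcting, the term is still undefined, and the 80% would then apply only to the pooled within-eye change.
- **The between-cohort powers are conditional.** They assume that 13 µm is also the group difference of interest, and the plan gives no expected keratoconus-versus-glaucoma difference. They also assume one value per subject, whereas the analysis uses both eyes of some subjects and the device section describes four pressure applications per eye. This stands. The 80% to 29% range is an illustration across readings, not a bound. Eye clustering and repeat measurements could change the effective variance, but they cannot close a 500-fold gap.
- **The headline factor depends on sidedness.** This also stands. One-sided, the factor runs from 39.5/0.07 = 564 to 79.1/0.07 = 1,129.
- **Arithmetic and target comparison are separate matters.** They are, but the second decides what a corrected SD means for the objective, so both belong in the same paragraph.
- **The defect biases no estimate.** This is a non-randomised physiology study, and the printed inputs imply too much power rather than too little. But they show only that the printed variability was not the one used. They give no assurance about actual power.

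**Conclusion.** The concern holds. The stated 80% does not follow from the stated inputs on any reading that keeps 0.07 µm. Used as an SD, it gives essentially 100%; used as measurement error, it leaves the calculation without an SD. For a two-sided 5% test with one value per subject, 80% power needs an SD of 35 to 70 µm, or 500 to 1,000 times the printed figure.

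The plan is not shown to be overpowered, nor is it shown to be too small. Its power for the named group comparison simply cannot be derived. If 13 µm is also the group difference of interest, the SDs that make some two-sided test reach 80% put that power anywhere from about 80% to about 29%. The failure to reproduce 80% does not depend on sidedness or on the unit-slip explanation. This should be corrected before the sample size is relied on.

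**What to change.** Rewrite the sample-size paragraph in Section 6:

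1. Take the variability figure from the pilot data, check its unit, and define it, for example as the SD of the within-subject change in cup depth.
2. Name the test and its sidedness, and say how two eyes from one subject were treated.
3. State whether 13 µm is the change within eyes or the difference between cohorts.
4. Give the power, or the difference detectable with 80% power, at 115 per cohort for both the within-cohort change and the keratoconus-versus-glaucoma comparison.
5. Justify 230 from the corrected figures, or revise it if they do not support it.

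The cost is one paragraph, using pilot data that the sponsor already cites. The correction itself needs no extra participants. The drawback is that the stated power for the group comparison may turn out lower. The sponsor would then have to accept a larger detectable difference or reconsider the sample size.
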